11/29/17

NCT01458990: Proton Pump Inhibitors and Dysbiosis in Cirrhosis

Protocol Outline for Decompensated cirrhosis portion of the study (the compensated cirrhosis and healthy control portion is published in AJP 2014 and the publication has been uploaded)

RESEARCH PLAN

This will be a prospective 14-day study of outpatients with decompensated cirrhosis (Study overview is presented in the figure). We will recruit subjects from the hepatology clinics at the McGuire VA and VCU Medical Center.

There will be two age-matched patient groups:

Group 1: Patients not on PPI therapy who will be started on omeprazole 40mg/Qday before breakfast

Group 2: Patients on 40mg/day omeprazole or equivalent for an unapproved indication who will be withdrawn from the PPI

Inclusion criteria for both groups:

1. Cirrhosis diagnosed using biopsy, or radiologic/endoscopic evidence of cirrhosis and/or varices in the setting of chronic liver disease.
2. Evidence of decompensation: ascites or hepatic hydrothorax by history, examination due to cirrhosis or controlled using diuretics, history of variceal bleeding or jaundice (bilirubin >5mg/dl) at time of enrollment.
3. Able to give consent

Exclusion criteria for both groups:

1. unclear diagnosis of cirrhosis or of decompensation
2. Alcohol/illicit drug use in the last 3 months
3. Unable to give consent
4. Current hepatic encephalopathy treatment (lactulose, rifaximin), SBP prophylaxis, probiotics
5. Recent (<2 months) infections or treatments with systemic antibiotics or upper GI bleed
6. Allergic to PPI therapy
7. Patients on H2 receptor blockers

Special inclusions/exclusions for Group 2: we will only consider cirrhotic patients on 40mg/day omeprazole equivalent for PPI withdrawal if they are

1. Willing to withdraw this therapy
2. Are on PPI therapy for an indication other than the FDA-approved ones listed below²²:
(a) Healing and maintenance of erosive esophagitis, (b) Treatment of gastro esophageal reflux disease, (c) Risk reduction for peptic ulcer with non-steroidal anti-inflammatory drugs (d) *Helicobacter pylori* eradication, in combination with antibiotics; (e) Pathological hyper-secretory conditions, including Zollinger-Ellison syndrome; (f) Short-term treatment and maintenance of peptic ulcer therapy.

Justification for study design and inclusion/exclusion criteria: our prior work and previous studies have shown that 14 days can change gut microbiota adequately with therapies. Since a large proportion of patients with decompensated cirrhotics are already on PPI, both a withdrawal and an introduction design will be used to increase the generalizability of the study results. We will exclude patients on recent/current antibiotics, probiotics and hepatic encephalopathy treatment to minimize the confounding factors for microbiota analysis. We chose 40mg/day before

breakfast since this was the dose the majority of our current decompensated cirrhotics are on and also to increase adherence with once-a-day dosing. Additionally this was also the regimen used in our preliminary study⁹.

Screening: we will bring potential patients in for re-confirming their eligibility, evaluation of their indication and adherence to PPI use and in those who potentially fall in group 2, to gauge their willingness to stop PPIs for 14 days. Once eligibility is confirmed and informed consent is obtained, a standard diet (35Kcal/kg/day and 1.2-1.5g/kg/day of protein) will be prescribed and a food diary will be issued. Subjects will be given stool collection kits (with RNAlater) and asked to return for visit 2 within 7-14 days after the first visit.

Visit 1: We will reconfirm eligibility and adherence. Blood will be collected for gastrin, calculation of MELD score, and metabolomics; stool will be collected for microbial composition and function; and urine will be collected for metabolomics. After collection of the specimens, patients from group 1 will be started on omeprazole 40mg/day before breakfast for 14 days while those in group 2 will be asked to withdraw their PPI therapy. All subjects will continue on the same diet. Subjects will be given the contact information of the study team in case they experience any change in their medications, urgent clinic visits, antibiotic use or hospitalizations in the interim. Subjects will be paid \$50 for completing the first visit activities and will be given a stool collection kit to bring with them for visit 2.

Telephone call one week after visit 1: to reconfirm that study conditions, diet conditions are being met and that there are no changes in the patients' underlying status. In case of initiation of antibiotics, change in PPI dose or re-initiation of PPI (group 2), we will attempt to bring those patients in as soon as possible to analyze microbiota changes.

Visit 2: At the end of 14 days, we will re-evaluate subjects' adherence on the study protocol and will perform all procedures regarding the study samples as in visit 1. At this point, the study participation for subjects will end. At this time, subjects will be paid \$125 for their participation.

Detailed analyses of samples: **Blood:** MELD score laboratories (bilirubin, INR, creatinine)²⁴ and will be analyzed through the VA hospital clinical laboratory. **Stool:** **Stool:** Stool in RNAlater will be used to extract both DNA and RNA at the MBAC at George Mason University, VA using published techniques.

Statistical analysis: in the separate document

Expected outcomes: We expect a significant change in microbiota function and composition with a reduction in dysbiosis and microbial genes activated towards formation of toxic metabolites and altered microbial-mammalian co-metabolites when PPIs are taken out of the patients' systems. We do not expect any additional adverse events, including infections to occur associated with PPI given the relatively short duration of the study but all complications will be noted. To ensure adequate numbers we are accounting for a 15% dropout rate. We will increase enrollment if there are more dropouts than planned.

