11/29/17

NCT01458990: Proton Pump Inhibitors and Dysbiosis in Cirrhosis

Safety analysis:

- A. Adverse events: related to PPI initiation (allergy, GI upset etc) or withdrawal (recurrence of symptoms, GI bleeding etc) will be analyzed using non-parametric tests.
- B. Withdrawal from study

Microbiota analysis:

Will be performed using multi-tagged sequencing of stool samples in pre vs post PPI (initiation) and before/after PPI withdrawal. Wilcoxon signed-rank matched pairs tests and Kruskal Wallis test will be used.

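### Does the SAP need a rule for which stool is the post value after an antibiotic start, a PPI dose change or a PPI restart?

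*Protocol*

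**What the plan says.** The protocol's one-week telephone call checks that study conditions still hold. It then provides for three events: "In case of initiation of antibiotics, change in PPI dose or re-initiation of PPI (group 2), we will attempt to bring those patients in", and this is to happen "as soon as possible to analyze microbiota changes". The next paragraph sets the scheduled follow-up, "Visit 2: At the end of 14 days", with the same sampling as at Visit 1. Neither paragraph says whether the early attendance replaces Visit 2 or is added to it.

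The SAP's Microbiota analysis section compares "stool samples in pre vs post PPI (initiation) and before/after PPI withdrawal". It names the Wilcoxon signed-rank test for matched pairs and the Kruskal-Wallis test, and does not rank one above the other. It does not define the post sample by visit or day, and it names no analysis set.

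Three other statements bear on the point:

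- The design justification says "We will exclude patients on recent/current antibiotics, probiotics and hepatic encephalopathy treatment to minimize the confounding factors for microbiota analysis".
- The Screening paragraph says patients are "asked to return for visit 2 within 7-14 days after the first visit".
- The Expected outcomes paragraph says "To ensure adequate numbers we are accounting for a 15% dropout rate" and allows extra enrolment if more patients than that are lost.

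**The concern.** A signed-rank test needs exactly one post value per patient. A patient who restarts a PPI on day 8, say, might give two stools after baseline, and the SAP does not choose between them. The possible choices answer different questions:

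- **Early stool as post:** a shorter exposure, sampled after the disturbing event.
- **Day-14 stool as post, whatever happened:** in Group 2, the effect of being asked to stop.
- **Patient left out:** the effect in those who kept to the assigned change.
- **Antibiotic-exposed stool kept:** an antibiotic effect mixed with the PPI effect.

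The events are not far-fetched. The SAP's safety section expects events related to PPI initiation "or withdrawal (recurrence of symptoms, GI bleeding etc", and such symptoms could lead to a restart, which can happen only in Group 2. The Screening sentence also seems to put Visit 2 at 7 to 14 days, while the Visit 2 paragraph puts it at day 14. On that reading, a stool taken soon after the one-week call might pass as the Visit 2 stool. With no written rule, the choice could be made after the sequencing results are known.

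**Working it through.** **1. Is there a default post sample?** The Screening sentence concerns the kit handed out at screening. The next stool is collected at Visit 1, and the Visit 1 paragraph issues a separate kit for Visit 2. The 7-to-14-day interval therefore fits screening to baseline, with screening counted as the first visit. The follow-up interval is fixed elsewhere: the study is described as lasting 14 days, Group 1 takes omeprazole for 14 days, and Visit 2 comes at day 14. The apparent conflict is a visit-numbering slip to be reconciled. It does not offer a second date for the post sample, so the day-14 stool is the only scheduled post value.

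**2. Do the antibiotic statements conflict?** Excluding antibiotic users at entry is compatible with sampling those who start later. The reason given for the exclusion, confounding, favours keeping antibiotic-exposed stool out of the PPI contrast, although it sets no rule.

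**3. Size for PPI restart.** The documents give no n, event rate, effect size or SD, so there is no figure of theirs to reproduce and every input here is assumed. Let a fraction f of patients restart and return fully to their earlier state. Required n varies as 1/(mean change)², ignoring the small extra spread from mixing the two kinds of patient.

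- Kept: the mean change is multiplied by (1 − f), so n is multiplied by 1/(1 − f)².
- Left out: the mean change is intact but patients are lost, so n is multiplied by 1/(1 − f).
- Kept relative to left out: 1/(1 − f)² ÷ 1/(1 − f) = 1/(1 − f).

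| f | Kept v no events | Left out v no events | Kept v left out |
|---|---|---|---|
| 0.05 | 1/0.9025 = 1.11 | 1/0.95 = 1.05 | 1.05 |
| 0.10 | 1/0.81 = 1.23 | 1/0.90 = 1.11 | 1.11 |
| 0.15 | 1/0.7225 = 1.38 | 1/0.85 = 1.18 | 1.18 |

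The last column measures the choice at issue. The first numeric column measures the cost of the events themselves, most of which no analysis rule can recover.

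Simulated power agrees. The setting was an exact two-sided 5% signed-rank test, n = 20, an effect of 0.68 SD giving 80% power with no events, and 40,000 replicates. Kept versus left out was 75% v 78%, 70% v 75% and 64% v 71% for the three fractions. With half return at 15%, it was 73% v 71%.

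**4. Size if the early stool is the post value.** Assume it shows half of a 0.8 SD effect (n = 20, 4,000 replicates). Power is 0.89 against 0.87 with the patients left out when 2 of 20 have an event, and 0.84 against 0.81 when 4 of 20 do. On this assumption the choice of stool barely matters.

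**5. Size for antibiotic-exposed stool.** Same setting as step 3, with a shift of 1 to 3 SD added to the exposed patients.

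| Starters of 20 | False positives, kept | Power, shift opposite to PPI effect | Power, same direction | Power, left out |
|---|---|---|---|---|
| 1 | about 5% | 72% to 56% | 84% to 86% | 78% |
| 2 | 6% to 8% | 63% to 26% | 87% to 90% | 75% |

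With 4 of 20 exposed and a 2 SD shift, the false-positive rate when they are kept is about 17%. This is where the choice could matter, and it is also where the protocol's own reasoning favours leaving the stool out.

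**The case for a change.** The strongest reply is that a default for which stool to use does not settle whether the patient stays in the test. Naming Visit 2 as the post visit leaves open whether a restarter's day-14 stool is kept, and the protocol does not say whether such patients count toward the 15% dropout. A restart can arise only in Group 2, so the choice could move one group alone. A paragraph in the SAP would cost little, and fixing the rule before results are seen is ordinary good practice.

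Much of this stands. The SAP has no rule, the estimands differ, and a choice made late is open to challenge. Three things limit its force:

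- Any such rule would be a preference. Keeping restarters and leaving them out are both defensible, and leaving out antibiotic starters selects on an event after baseline. A rule that could fairly be reversed does not correct an error.
- The link from recurrent symptoms to a restart is inference. The documents do not state it, and Group 2 excludes patients who take the PPI for reflux disease or ulcer.
- The early stool is implied rather than stated, and attendance is only to be attempted. Keeping the day-14 stool as post adds no data collection only if these patients also attend at day 14, which the protocol does not confirm.

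**Conclusion.** No change to the plan is called for. The SAP leaves a detail unwritten, and the protocol supplies most of what is needed to fill it: one scheduled post sample at day 14, and a stated reason to keep antibiotic exposure out of the microbiota comparison. The Screening sentence is a clerical slip in visit numbering. It can be reconciled editorially and has no bearing on the analysis.

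The choice left open, to keep or leave out patients who restart or change dose, is a fair trade-off. For restart it is modest in size: a factor of 1.05 to 1.18 in enrolment for restart in 5% to 15% of patients with full return, and next to nothing with half return. Dose change was not modelled separately. Leaving out 15% costs the same 1/0.85 = 1.18 as the planned dropout, and the protocol allows more enrolment if losses exceed plan, although it does not say that these patients count as losses.

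The large distortions need two or more antibiotic starters in a group within two weeks and shifts of 2 to 3 SD. All of these are assumptions, and so are the group size and the PPI effect. Many such events in practice would make the handling material. A report that gives event counts by group and names the post sample would let readers judge that.

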11/29/17

NCT01458990: Proton Pump Inhibitors and Dysbiosis in Cirrhosis

Safety analysis:

- A. Adverse events: related to PPI initiation (allergy, GI upset etc) or withdrawal (recurrence of symptoms, GI bleeding etc) will be analyzed using non-parametric tests.
- B. Withdrawal from study

Microbiota analysis:

Will be performed using multi-tagged sequencing of stool samples in pre vs post PPI (initiation) and before/after PPI withdrawal. Wilcoxon signed-rank matched pairs tests and Kruskal Wallis test will be used.

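### SAP item A can be read as limiting the adverse-event analysis to PPI-related events, and it plans tests without event frequencies (minor; cheap to fix)

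*SAP*

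**What the plan says.** **Protocol, Expected outcomes.** "We do not expect any additional adverse events, including infections to occur associated with PPI", because the study is short; the same sentence adds that "all complications will be noted". The expectation therefore concerns PPI-associated events. It is not a claim that no adverse events of any kind will occur.

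**Protocol, Visit 1 and the one-week telephone call.** Patients are given contact details for reporting a change in medication, "urgent clinic visits, antibiotic use or hospitalizations in the interim". The call checks for changes in the patient's underlying status. Patients who start antibiotics, change PPI dose or (Group 2) restart a PPI are to be brought in early if possible, for microbiota sampling.

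**Protocol, analysis.** "Statistical analysis: in the separate document".

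**SAP, Safety analysis, item A.** "Adverse events: related to PPI initiation (allergy, GI upset etc) or withdrawal (recurrence of symptoms, GI bleeding etc) will be analyzed using non-parametric tests".

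**SAP, Safety analysis, item B.** The whole item is "Withdrawal from study". It has no definition, summary or method.

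The Wilcoxon signed-rank and Kruskal-Wallis tests are named only under Microbiota analysis. No test is named for safety.

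**The concern.** The protocol records every complication, but the SAP sentence that analyses adverse events carries a relatedness phrase. Two analysts could build different safety tables from it. One would include everything that happened after the PPI change, sorted by whether the patient started or stopped. The other would include only events someone had judged to be caused by the change.

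The difference matters most for infections. Infection is the one event type that the protocol names in its safety expectation, and it is not among item A's examples. Whoever attributes an event will normally know whether the patient started or stopped a PPI, since the documents describe no blinding. A finding of no PPI-associated infections would then depend on that judgement, and the reader could not set it against all infections recorded.

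Separately, item A's only stated output is a test. In a 14-day study with few events, the number and percentage of patients affected, and the rate that the data rule out, tell a reader more than a p-value.

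**Working it through.** The plan has no safety figure to reproduce. It gives no group size, event rate, alpha or named safety test. The check is therefore a reading of the text, followed by a precision calculation on assumed group sizes.

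**Step 1. Follow three patients through the SAP under each reading.**

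| Noted event after the Visit 1 PPI change | *Related to* is a filter | *Related to* sorts by group |
|---|---|---|
| GI upset after starting, judged related | Item A | Item A |
| Infection judged unrelated; patient completes Visit 2 | Neither item | Item A |
| Hospitalisation judged unrelated; ends participation | Item B, as a withdrawal, no method stated | Item A and item B |

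Under the filter reading, the second patient appears in no planned safety result. Under the sorting reading, nothing is lost.

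**Step 2. What a test shows with no events.** Item A does not name a comparison. For a between-group test with no events of a type in either group, only one 2×2 table is possible, so p = 1 at any group size. A before-and-after test has no discordant pairs and nothing to test. In neither case does the result depend on how large a rate the data exclude.

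**Step 3. What an exact interval shows.** The limits are Clopper-Pearson two-sided 95% upper limits. Group sizes of 10, 20 and 50 are assumptions.

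- Zero events: upper limit = 1 − 0.025^(1/n).
- One patient with an event: upper limit = 0.975 quantile of Beta(2, n − 1).

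| n per group (assumed) | 0/n: upper limit | 1/n: proportion | 1/n: upper limit |
|---|---|---|---|
| 10 | 1 − 0.025^(1/10) = 30.8% | 10% | 44.5% |
| 20 | 1 − 0.025^(1/20) = 16.8% | 5% | 24.9% |
| 50 | 1 − 0.025^(1/50) = 7.1% | 2% | 10.6% |

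The zero-event column is what a bare test hides. With 10 patients and no events, true rates up to about 31% remain compatible with the data; with 50 patients, up to about 7%.

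The two upper-limit columns together show the effect of filtering out one patient whose only event was judged unrelated. The reported proportion falls from 1/n to zero, and the upper limit falls from 44.5% to 30.8%, from 24.9% to 16.8%, or from 10.6% to 7.1%. This shows sensitivity to one patient. It does not forecast how many would be omitted.

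**The case against.** The best case for the plan is that *related to* is only a sorting phrase. Item A gives one list of examples for initiation and one for withdrawal, matching Groups 1 and 2. Both lists are left open, and a causal filter with no causality procedure would be odd. This is plausible, and if it is what the sponsor means, no event is excluded. But the SAP does not say so, and the literal wording supports the other reading equally well.

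A second objection is that nobody can test adverse events without counting them, and that the SAP does not forbid a table. That is true, but it leaves the denominator, the grouping and the handling of unrelated events to be settled after the data are seen. Item B has no method at all.

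A third is that this is a short study, described in an outline, whose expected outcomes concern microbiota. That stands. No microbiota conclusion changes, which is why the point is minor.

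Some stronger inferences are tempting but unsupported:

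- *The SAP contradicts the protocol or discards unrelated events.* The documents show an ambiguity between what is recorded and what is analysed. They do not state an exclusion.
- *The protocol predicts no adverse events at all.* The expectation is limited to PPI-associated events, which is close to item A's own scope.
- *The dropout allowance shows how many patients item B will hold.* The protocol says "To ensure adequate numbers we are accounting for a 15% dropout rate". That is an enrolment allowance with no timing. Some dropouts could occur between screening and Visit 1, before any PPI change.
- *Events would not reach the study team.* The contact list and the one-week call are reasonable routes for collection, even though they partly serve microbiota follow-up. The gap is in analysis.

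**Conclusion.** The point holds as a minor one. Item A's wording permits a filter on relatedness, no rule for relatedness is given, and no passage says how other noted complications are to be summarised. Whether any event would be lost depends on a reading that the documents do not settle, and they give no basis for estimating how many.

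The second part holds under either reading: the only method stated for adverse events is an unnamed test, which says little when events are few or absent. The size of that gap is the range of zero-event upper limits, 7.1% to 30.8%. It rests wholly on the assumed 10 to 50 patients per group and on exact two-sided 95% intervals. No event rate is assumed.

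**What to change.** Replace item A with wording such as:

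> All adverse events and complications noted from the Visit 1 PPI change until Visit 2, early-return visit or last contact, whichever ends participation, will be tabulated by group and type regardless of relatedness, including infections, GI bleeding and hospitalisations, with number and percent of patients and an exact 95% CI per group. The denominator is all patients who made the Visit 1 PPI change. Any test is secondary.

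The end-point of the window is worded to cover patients who never reach Visit 2 or who are brought in early. If the sponsor also wants to show relatedness, the SAP should say who assigns it and by what rule.

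Complete item B as: number and percent withdrawn, by group and reason.

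The cost is SAP wording and one extra table, built from complications that the protocol already says will be noted. No patients, visits or samples are added. The downside is that the intervals will be wide in small groups.

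### The unspecified adverse-event test in SAP item A cannot show that starting or stopping a PPI is safe; per-group proportions with exact intervals should replace it

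*SAP*

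**What the plan says.** SAP, Safety analysis, item A: adverse events "related to PPI initiation (allergy, GI upset etc) or withdrawal (recurrence of symptoms, GI bleeding etc) will be analyzed using non-parametric tests". No test, endpoint form, contrast or null is given. The signed-rank and Kruskal-Wallis tests, and the before/after contrasts within each group, appear only in the SAP's Microbiota analysis paragraph.

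Protocol, Research Plan: "There will be two age-matched patient groups". Group 1 is "Patients not on PPI therapy who will be started on omeprazole 40mg/Qday before breakfast"; Group 2 is "Patients on 40mg/day omeprazole or equivalent for an unapproved indication who will be withdrawn from the PPI". Both change at Visit 1: Group 1 begins omeprazole after the specimens are taken, "while those in group 2 will be asked to withdraw their PPI therapy". Follow-up is two weeks: "At the end of 14 days, we will re-evaluate subjects' adherence on the study protocol".

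The described routes for learning of events begin at or after the switch. They are study-team contact details handed out at Visit 1, a telephone call a week later, and a general statement under Expected outcomes that complications will be recorded. The Visit 1 paragraph covers eligibility, adherence and specimens, but no event or symptom count. Expected outcomes also states: "We do not expect any additional adverse events, including infections to occur associated with PPI".

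The documents give no group size, event rate or significance level. The only planning figure is the 15% dropout allowance.

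**The concern.** Item A puts two different harms on one line. Initiation events can arise only in Group 1 and withdrawal events only in Group 2. The useful safety question is how often each switch is followed by harm, and whether that exceeds what would have happened without it. The second part needs a comparator whose PPI status does not change, and the design describes none.

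A p-value will still be produced if item A is followed. The likely misuse is to set a non-significant result beside the protocol's expectation of no extra events and treat the two as agreeing. The patients have decompensated cirrhosis, and item A itself lists GI bleeding among the possible consequences of withdrawal, so unfounded reassurance would matter.

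**Working it through.** **Inputs.** From the documents: two groups, opposite switches at the same visit, 14 days of follow-up, no unswitched group, and no described baseline event count. There is no stated figure to reproduce. Assumed for illustration: two-sided alpha 0.05; 15, 20, 30 or 50 patients per group; endpoint is at least one event per patient; true rates as shown.

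**Step 1: what can be tested.**

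| Comparison | Null hypothesis | Does it address extra harm from a switch? |
|---|---|---|
| Group 1 vs Group 2 | Rate after starting = rate after stopping | No |
| Before vs after within a group, switch-related events | Affected patients equally likely before and after | No; the count before is zero by definition |
| Each group alone | None needed | Estimates the rate; does not isolate the excess |

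**Step 2: equal rates.** With n per group and i and j affected patients, the rejection probability is the sum over all i and j of Bin(i; n, p1) × Bin(j; n, p2), counting only the pairs that the test rejects. The tests are Fisher's exact test and Kruskal-Wallis on 0/1 data. With N = 2n and s = i + j, the latter is H = (N − 1)[i(n − j) − j(n − i)]² / [n² s(N − s)], rejecting at 3.841 or more.

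A single case shows the problem. With 6/20 affected in each group, the bracket is 6 × 14 − 6 × 14 = 0, so H = 0 and p = 1, although 30% of patients in both groups had an event.

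Rejection probabilities when both groups share one rate (Fisher / Kruskal-Wallis):

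| n per group | 5% | 10% | 30% | 50% |
|---|---|---|---|---|
| 15 | 0.001 / 0.005 | 0.005 / 0.024 | 0.017 / 0.040 | 0.017 / 0.043 |
| 20 | 0.002 / 0.012 | 0.012 / 0.039 | 0.025 / 0.053 | 0.020 / 0.043 |
| 30 | 0.001 / 0.028 | 0.009 / 0.054 | 0.026 / 0.049 | 0.027 / 0.052 |
| 50 | 0.007 / 0.043 | 0.018 / 0.048 | 0.031 / 0.050 | 0.035 / 0.057 |

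The result stays near alpha or below it whether 5% or 50% are affected, and a larger group does not change that.

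**Step 3: unequal rates** (Fisher, n = 15 / 20 / 30).
- 20% vs 30%: 0.040 / 0.062 / 0.089
- 10% vs 30%: 0.149 / 0.242 / 0.372
- 10% vs 50%: 0.536 / 0.742 / 0.914

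A large difference can be detected, but it says only that one switch was followed by more events than the other. It does not say that the group with the lower rate is free of harm.

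**Step 4: a paired test.** With no events before the switch and k affected patients after it, the two-sided sign (exact McNemar) p-value is 2 × 0.5^k: 0.0625 at k = 5 and 0.031 at k = 6. Group size does not enter. Six affected patients give the same p in a group of 15 (6/15 = 40%) as in a group of 50 (6/50 = 12%). The test registers that events occurred, not that they exceed a background rate.

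**Step 5: what each group can show alone.** The Clopper-Pearson 95% limits are the 0.025 quantile of Beta(x, n − x + 1) and the 0.975 quantile of Beta(x + 1, n − x). For x = 0 the upper limit is 1 − 0.025^(1/n).

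| n | Events near 30% | 95% interval | Upper limit with zero events |
|---|---|---|---|
| 15 | 4/15 | 7.8% to 55.1% | 21.8% |
| 20 | 6/20 | 11.9% to 54.3% | 16.8% |
| 30 | 9/30 | 14.7% to 49.4% | 11.6% |

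**The case against.** The strongest reply is that the SAP never commits to starters versus stoppers. It names no contrast, and non-parametric tests include within-group ones, which the same document plans for microbiota. This stands: a reader might infer that item A can only mean a between-group test, and the text does not say so. The within-group reading does not rescue item A, however, for the reason in Step 4.

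A second reply is that equal rates make the null true by construction, so a rejection rate near alpha is no discovery. That is correct, and it is the point: the null can be exactly true while both switches do harm. A reader might go further and say that harm from the two switches always cancels. Step 3 shows that it does so only to the extent that the rates are similar.

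A third reply is that the protocol's expectation concerns events associated with PPI use, which is an on-versus-off question that Group 1 against Group 2 partly addresses, and that no decision hangs on an adverse-event p-value. This has force for infections. It does not reach the withdrawal symptoms and bleeding that item A lists, which arise from stopping. It is also true that the documents state no safety hypothesis, so the misreading is a risk and not a planned conclusion.

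**Conclusion.** The point holds in this form: item A promises a test without a contrast, and neither the between-group test nor a paired test of switch-related events can show that starting or stopping is safe. For equal rates the rejection probability is at most 0.035 (Fisher) or 0.057 (Kruskal-Wallis) over rates of 5% to 50% and 15 to 50 patients per group. These sizes, rates and alpha are assumptions. The conclusion about the null does not depend on them, because it follows from the two-group, opposite-switch design.

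It would be tempting to express the damage as power lost against a comparison with patients who did not switch. The documents do not support such a figure, since neither the design nor the remedy contains an unswitched group. The point concerns the safety analysis only; the expected outcomes lead with microbiota, and that analysis is unaffected. The SAP should be changed, because a better method is available at almost no cost.

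**What to change.** Replace the test in item A with separate reporting: initiation events in Group 1 and withdrawal events in Group 2, each as n/N with an exact (Clopper-Pearson) 95% interval. Word any statement that no extra events were seen as the rate excluded. For example, with 0/20 the data exclude rates above 16.8%.

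State that a Group 1 versus Group 2 p-value will not be used as evidence that starting or stopping is safe. If that contrast is kept for infections (on versus off PPI), give it as a difference with an interval.

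A comparison with the period before Visit 1 should be descriptive at most, limited to symptoms such as GI upset, and would need those symptoms to be asked about at Visit 1. It cannot serve for bleeding or infection: exclusion criterion 5 bars recent infection and upper GI bleeding, and eligibility is rechecked at Visit 1, so patients with such events are removed and the earlier count is pushed towards zero. The length of that period is also unclear. The Screening paragraph labels the return after 7 to 14 days as visit 2, while the later Visit 2 paragraph describes the end of the 14 study days; the two need to be reconciled.

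The cost is a short SAP revision, with no added patients or visits. The downside is wide intervals and no p-value for safety.
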